1.5 Study Design

This is a Phase Ib multi-centre study investigating AZD1775 monotherapy in patients with locally advanced or metastatic solid tumours. The study will evaluate the safety and the Maximum Tolerated Dose (MTD)/Recommended Phase 2 Dose (RP2D) of AZD1775 in patients for which standard therapy does not exist or has proven ineffective or intolerable. AZD1775 will be taken by mouth (PO) once a day (QD) or twice daily (BID) on a 5/9 dosing schedule every 14 days (dosing on days 1 to 5, followed by no treatment on days 6-14), QD on a 5/2 dosing schedule every 21 days (dosing on days 1 to 5, no treatment on days 6-7, then dosing again on days 8 to 12, followed by no treatment on days 13-21), or QD on a 5/2 weekly dosing schedule every 21 days (dosing on days 1 to 5, no treatment on days 6-7, dosing on days 8 to 12, no treatment on days 13-14, dosing on days 15 to 19, followed by no treatment on days 20-21). Treatment cycles are 14 (schedule 5/9) or 21 (schedule 5/2) days. The patients already enrolled and treated on the BID schedule will continue on the assigned regimen. Dosing cohorts are shown in [Table 1](#).

For patients currently on the BID dosing schedule ([Figure 1](#) and [Figure 2](#)), AZD1775 PO will be administered in approximate 12 hour intervals BID over 5 days (10 doses) on Days 1 through 5 followed by 9 days of no dosing. Treatment cycles will be repeated every 14 days.

For patients on the QD dosing schedule, the AZD1775 MTD will be determined through dose-escalation using a 3+3 cohort design. Initially, 3 patients will be enrolled and treated at the start of each cohort. However, to allow for any unforeseen discontinuations before the dose-limiting toxicity (DLT) period is completed, an extra patient may be enrolled and treated at each dose escalation cohort. Therefore, there may be a total of 4 patients (3 + 1) at the start of each cohort, provided that the 4th patient is able to start the first day of dosing within approximately 1 week of the 3rd patient in the same dose escalation cohort.

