- n For the fed condition, which requires the consumption of a high-fat meal (see Section 7.3), patients will be required to fast for ≥ 10 hours prior to receiving AZD1775 until 4 hours post-dose, with the exception of a high-fat meal that should be eaten in the 30 minutes prior to AZD1775 being administered on Cycle 2 Day 1. The AZD1775 capsule should be administered 30 minutes after the start of meal consumption. If the meal is not completed within 30 minutes, AZD1775 may still be administered so long as 75% of the meal has been consumed within 45 minutes of the start of the meal (see Section 7.3).
- o Initial (i.e. baseline) tumour imaging studies (e.g. computed tomography (CT) scan of the chest and abdomen/pelvis) will be performed within 28 days prior to the first dose of study drug (AZD1775) and will be repeated at the completion of Cycle 4 (Week 8) within 7 days before starting Cycle 5. Patients with measurable or non-measurable disease will be evaluated according the RECIST v1.1. Patients with progressive disease or unacceptable toxicity should be discontinued from the study; patients with stable disease or response to therapy will continue treatment. The same method of assessment and the same technique must be used to characterize each identified and reported lesion at screening/baseline and during subsequent imaging procedures. Tumour imaging studies will be repeated every 4 cycles (8 weeks) to assess response.
- p Blood samples will be taken for plasma isolation before dosing on Cycle 1 Day 1, Cycle 2 Day 1, Cycle 3 Day 1, and on Day 1 of every 2 cycles afterwards (e.g. Cycles 5, 7 [see Section 5.5]).
- q Patients without evidence of undue toxicity may continue treatment with study drug until disease progression as long as the investigator deems that the patient is deriving clinical benefit and desires to continue therapy.
- r Patients discontinuing AZD1775 should be scheduled for an end of treatment (EOT) study visit as soon as possible after their last dose (< 30 days after finishing study treatment). If treatment is discontinued during a study visit, the EOT visit does not need to be repeated. The reason for stopping treatment and date must be recorded in the electronic case report form (eCRF).

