- q Initial (i.e. baseline) tumour imaging assessments (e.g. computed tomography (CT) scan of the chest and abdomen/pelvis) will be performed within 28 days prior to the first dose of study drug (AZD1775) and repeated every 8 weeks (± 1 week) relative to the date of first dose until disease progression. Patients with measurable or non-measurable disease will be evaluated according to RECIST v1.1. The same method of assessment and the same technique must be used to characterize each identified and reported lesion at screening/baseline and during subsequent imaging procedures.
- r Blood samples will be taken for plasma isolation before dosing on Cycle 1 Day 1, Cycle 2 Day 1, Cycle 3 Day 1, Cycle 4 Day 1, and on Day 1 of every 2 cycles afterwards (e.g. Cycles 6, 8 [see Section 5.5]), EOT and FPV. Patients continuing treatment after FPV will have a plasma sample collected at the time of progression.
- s Patients without evidence of undue toxicity may continue treatment with study drug until disease progression as long as the investigator deems that the patient is deriving clinical benefit and desires to continue therapy.
- t Patients discontinuing AZD1775 should be scheduled for an end of treatment (EOT) study visit as soon as possible after their last dose (< 30 days after finishing study treatment). If treatment is discontinued during a study visit, the EOT visit does not need to be repeated. The reason for stopping treatment and date must be recorded in the electronic case report form (eCRF). The EOT visit is **not** required for subjects continuing treatment after the FPV. The FPV should be considered as the patient's next cycle scheduled visit after the implementation of CSP Version 5.
- u All patients will be followed during the off-treatment period until all treatment related toxicity resolves, or for at least 30 days post-study drug discontinuation or until new therapy. This can be done via telephone contact at the Investigator's discretion. All concomitant medications received 30 days after the last dose of study medication(s) should be recorded in the medical record and eCRF.
- v AZD1775 PO QD, over 5 days, on Days 1-5 every 14 days. AZD1775 should be taken under fasting conditions with 8 ounces of water approximately 2 hours before or after food.

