5.1 Efficacy assessments

5.1.1 Tumour assessments

RECIST v1.1 criteria will be used to assess patient response to treatment. The RECIST v1.1 guidelines for measurable, non-measurable, target lesions (TL) and non-target lesions (NTL) and the objective tumour response criteria (Complete Response [CR], Partial Response [PR], Stable Disease [SD] or progressive disease [PD]) are presented in [Appendix E](#).

The same method of assessment of tumour burden used at baseline (CT scans or magnetic resonance imaging [MRI] of the chest and abdomen/pelvis) must be used at each subsequent follow-up assessment (see [Table 2](#), [Table 3](#), and [Table 4](#)). Tumour imaging studies will be repeated every 8 weeks (± 1 week) relative to date of first dose for patients on the QD 5/9 treatment schema and every 9 weeks (± 1 week) relative to date of first dose for patients on the QD 5/2 treatment schema to assess response until objective disease progression as defined by RECIST v1.1 or withdrawal from study.

Categorisation of objective tumour response assessment will be based on the RECIST v1.1 criteria of response: CR, PR, SD and PD. Target lesion progression will be calculated in comparison to when the tumour burden was at a minimum (i.e. smallest sum of longest diameters previously recorded on study). In the absence of progression, tumour response (CR, PR, or SD) will be calculated in comparison to the baseline tumour measurements obtained before starting treatment.

If the Investigator is in doubt as to whether progression has occurred, particularly with regard to NTLs or the appearance of a new lesion, it is advisable to continue treatment until the next scheduled assessment or sooner if clinically indicated, and reassess the patient's status. If repeat scans confirm progression, then the date of the initial scan should be declared as the date of progression.

To achieve 'unequivocal progression' on the basis of non-target disease, there must be an overall level of substantial worsening in non-target disease such that, even in presence of SD or PR in target disease, the overall tumour burden has increased sufficiently to merit discontinuation of therapy. A modest 'increase' in the size of one or more NTL is usually not sufficient to qualify for unequivocal progression status.

It is important to follow the assessment schedule as closely as possible.

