6.7.2 Dose modifications due to haematologic toxicity

Complete blood counts (CBC) will be obtained for all patients at the beginning of each treatment cycle (Day 1). If haematologic toxicity occurs (see [Table 9](#)), treatment should be held and ANC and platelets should be monitored weekly until recovery.

Table 9 Cycle Day 1 Haematologic Dose Modifications

Treatment Day Blood Counts and Toxicity			
ANC		Platelets	Action
≥1000/μL	And	≥75,000/μL	No dose modification or interruption
<1000/μL	Or	<75,000/μL	Delay by 1 week intervals until recovery

If haematologic toxicity parameters do not recover within 21 days, the patient should be removed from the study treatment.

Table 10 Neutropenia, Infection, Febrile Neutropenia Dose Modifications and Management

Any Day	

Grade 3 neutropenic fever (ANC <1000/μL + Temperature \geq101°F [38.5°C]) or neutropenic infection
 
Documented infection with Grade 3 neutropenia (ANC <1000/μL)
 
Grade 4 neutropenia (ANC <500/μL >7 days)
 
Grade 4 thrombocytopenia (platelet count <25,000/μL >7 days)
	
Hold dose until recovery.
 
Then, upon resuming dosing, reduce AZD1775 to the next lower dose level^a.

Grade 4 febrile neutropenia or Grade 4 infection with neutropenia (both defined as septic shock)
 
Thrombocytopenic haemorrhage (gross occult bleeding) associated with a platelet count <50,000/μL
	
Discontinue treatment and follow for disease progression.

a No more than two dose reductions will be allowed for any patient. Patients requiring additional dose modifications due to toxicity will discontinue study treatment.

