8.4.5 Best objective response

The best objective response to treatment via RECIST v1.1 and Investigator assessment will be summarised by dose level cohort.

The best objective response (BOR) per subject will be derived as the best response recorded from the start of treatment until disease progression, death or subsequent cancer therapy (taking as reference for progressive disease the smallest measurements recorded since treatment started) using the Investigator reported objective response per time point. See [Appendix E](#) for how objective visit responses will be recorded.

Objective Response Rate (ORR) is the proportion of patients whose confirmed best objective response is complete response (CR) or partial response (PR). Confirmation must occur at least 4 weeks later.

Only patients with measurable disease will be included in the analysis of ORR. Patients without measureable disease at baseline will be excluded in the analysis of ORR.

The following rules will be used to determine the best objective response in each patient, assuming Assessment 1 is Baseline/Pre-treatment tumour assessment, and assessments are performed every 8 weeks on the BID and QD 5/9 Schedule or 9 weeks on either of the 5/2 Schedules.

Assessment 2	Assessment 3	Assessment 4	Best Objective Response
PD	-	-	PD
CR, PR, SD	PD	-	SD
UNK	PD	-	PD
CR, PR or SD	UNK	PD or UNK	SD
SD or UNK	CR, PR or SD	PD	SD
UNK	UNK	PD	PD

Assessment 2	Assessment 3	Assessment 4	Best Objective Response
PR	SD ⁽¹⁾	PD	SD
PR	CR or PR	PD or UNK	PR
PR	SD	PR	PR
PR	UNK	PR	PR
CR	CR	PD	CR
CR	UNK	CR	CR

(1) Only if the increase in diameter from Assessment 2 to Assessment 3 does not qualify for PD

- **Objective Response Rate (ORR)** = Proportion of patients with a confirmed best objective response of CR or PR.

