Baseline assessments should encompass chest, abdomen and pelvis and should additionally investigate areas that may be involved based on signs and symptoms of individual patients and should be performed no more than 28 days before the start of study treatment. Follow-up assessments will be performed every 8-9 weeks (depending on the dosing schedule) +/- 1 week window interval after start of treatment until objective disease progression as defined by RECIST 1.1, or withdrawal from study Any other sites at which new disease is suspected should also be adequately imaged at follow-up.

If an unscheduled assessment was performed and the patient has not progressed, every attempt should be made to perform the subsequent assessments at their scheduled visits. This schedule is to be followed in order to minimise any unintentional bias caused by some patients being assessed at a different frequency than other patients.

Target Lesions (TA)

Documentation of target lesions

A maximum of 5 measurable lesions, with a maximum of 2 lesions per organ (including lymph nodes), representative of all lesions involved should be identified as TL at baseline. Target lesions should be selected on the basis of their size (longest diameter for non-nodal lesions or short axis for nodal lesions), but in addition should be those that lend themselves to reproducible repeated measurements. It may be the case that, on occasion, the largest lesion does not lend itself to reproducible measurement in which circumstance the next largest lesion, which can be measured reproducibly, should be selected.

The site and location of each TL should be documented as well as the longest diameter for non-nodal lesions (or short axis for lymph nodes). All measurements should be recorded in millimeters. At baseline the sum of the diameters for all TL will be calculated and reported as the baseline sum of diameters. At follow-up visits the sum of diameters for all TL will be calculated and reported as the follow-up sum of diameters.

Special cases:

- For TL measurable in 2 or 3 dimensions, always report the longest diameter. For pathological lymph nodes measurable in 2 or 3 dimensions, always report the short axis.
- If the CT/MRI slice thickness used is $> 5\text{mm}$, the minimum size of measurable disease at baseline should be twice the slice thickness of the baseline scan.
- If a lesion has completely disappeared, the longest diameter should be recorded as 0 mm.

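### Table 2 footnote o times BID tumour scans by completed cycles, against the protocol's own calendar rules, so after about two weeks of dose delay the scan date depends on toxicity and can change SD to PD

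*Protocol*

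**What the plan says.** **Cycle rule, BID.** Section 4, Table 2 footnote o, says that the first post-baseline imaging "will be repeated at the completion of Cycle 4 (Week 8) within 7 days before starting Cycle 5". For later scans it says: "Tumour imaging studies will be repeated every 4 cycles (8 weeks) to assess response".

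**Calendar rules that reach BID.**
- The scan marks in Table 2 stand under a column headed every 8 weeks, with a window of 7 days either side.
- Appendix E, under the schedule of evaluation, covers all regimens: "Follow-up assessments will be performed every 8-9 weeks (depending on the dosing schedule"), with a window of 1 week either side, counted from the start of treatment. It gives as its reason the avoidance of bias from patients being assessed at different frequencies.
- Section 8.4.5 builds its best-response table on the premise that "assessments are performed every 8 weeks on the BID and QD 5/9 Schedule".

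**Calendar rules for QD only.** Footnote q of Tables 3 and 4 sets scans every 8 or 9 weeks "relative to the date of first dose until disease progression". Section 5.1.1 uses the same anchor, "relative to date of first dose for patients on the QD 5/9 treatment schema" and likewise for QD 5/2, and gives no BID schedule.

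**Delays.** Section 1.5 says of BID: "Treatment cycles will be repeated every 14 days". Table 9 says of low counts on Day 1 of a cycle: "Delay by 1 week intervals until recovery". Under Section 6.7, a single toxicity delay leads to discontinuation only beyond 21 days, unless the Medical Monitor approves continuation.

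**The concern.** A scan tied to the end of Cycle 4 moves whenever a cycle moves, and cycles move because of toxicity. A scan tied to the first dose does not. The protocol gives BID patients both instructions, and the detailed one is the cycle rule. A site following footnote o therefore scans a patient with delays later than a site following the column header.

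The date of the first scan matters for best response, which is a secondary outcome summarised by dose cohort. In the Section 8.4.5 table, PD at the first post-baseline scan gives a best response of PD, whereas SD followed by PD gives SD. The protocol sets no minimum duration for SD, and disease control (Section 8.3.1) counts SD. A patient who progresses between the calendar date and the delayed date can therefore change category because of scan timing alone. This is the unequal assessment that Appendix E sets out to avoid.

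**Working it through.** **Inputs.** BID cycle of 14 days (1.5). Footnote o scan in the 7 days before Cycle 5. Calendar window of 8 weeks plus or minus 7 days (Table 2 header), that is days 49-63. Delays in 1-week steps (Table 9). A 53-day limit for BID (8.4.6). First dose is taken as day 0, and the 1-day cycle windows are ignored.

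**Step 1: the plan's own figure.** 4 x 14 = 56 days = 8 weeks. The footnote's equation of four cycles with 8 weeks is right when there is no delay.

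**Step 2: scan window under delay.** With cumulative delay d, Cycle 5 starts on day 56 + d, so the footnote window is day 49 + d to day 56 + d.

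| d (days) | Footnote o window | Days inside 49-63 | Latest scan past day 63 by |
|---|---|---|---|
| 0 | 49-56 | 8 of 8 | 0 |
| 7 | 56-63 | 8 of 8 | 0 |
| 14 | 63-70 | 1 of 8 | 7 days |
| 21 | 70-77 | 0 of 8 | 14 days |

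A one-week delay does no harm. The rules part at about two weeks and separate fully at three. The 21-day limit applies to each delay, so several delays could add up to more.

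**Step 3: SD against PD.** The protocol gives neither a median PFS nor a frequency of delay, so this step is illustrative. Assume exponential PFS and a scan on the last permitted day. The share progression-free at the first scan is 2^(-t/median).

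| Assumed median | Week 8 | Week 10 (d = 14) | Week 11 (d = 21) |
|---|---|---|---|
| 8 weeks | 0.50 | 0.42 | 0.39 |
| 12 weeks | 0.63 | 0.56 | 0.53 |
| 16 weeks | 0.71 | 0.65 | 0.62 |

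The fall from week 8 to week 11 is 0.09 to 0.11. If all 12 BID patients were delayed by three weeks, that would be about 12 x 0.09 = 1.1 to 12 x 0.11 = 1.3 patients reclassified. With fewer delayed patients, or scans earlier in the window, it would be less.

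**Step 4: recorded PFS.** Section 8.4.6 censors a BID patient at Day 1 if there is neither a post-baseline scan nor death within 53 days. It censors PD or death more than 53 days after the previous CR, PR or SD scan back to that scan.
- No delay: 3 of the 8 permitted days (54-56) are already past day 53.
- Delay of 7 days or more: every permitted day is past day 53, so the text censors the patient at Day 1 unless death comes first.
- Later scans: the nominal spacing is 56 days without delay, and 63, 70 or 77 days with it. All exceed 53, so a PD found at the next scan is censored back.

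The limits are described as 2.5 assessment intervals, but they match cycle lengths: 2.5 x 21 = 52.5 and 2.5 x 14 = 35. With real scan intervals they would be 2.5 x 56 = 140 and 2.5 x 63 = 157.5 days. Only under a limit of about 140 days would a delay of 7-21 days yield a PFS event dated later, by up to about that much.

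**Step 5: does re-anchoring repair PFS?** No. In the calendar window of days 49-63, 10 of 15 days (54-63) are still past day 53.

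**The case against.** The strongest reply is that Table 2 is not a pure cycle rule. Its header is in calendar time, footnote o itself adds the 8-week equivalents, and Appendix E and Section 8.4.5 also cover BID. A reader could take the cycle wording as shorthand. This stands to the extent that BID is not left with the cycle rule alone. It does not remove the contradiction, because footnote o fixes the scan by the start of Cycle 5 and nothing says which statement governs when the two differ.

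A second reply concerns reach. Table 2 is closed to enrolment, Table 12 marks both BID cohorts as completed, the Final Protocol Visit appears only in Tables 3 and 4, and Section 8.4 plans no formal testing and no further statistical analysis after the primary cut-off. PFS is not a listed outcome measure. QD 5/2 is scanned every 9 weeks by design, so the cohorts would not share one scan schedule even after a correction. All of this stands and keeps the point small. Against it, the Synopsis and Section 1.5 say that BID patients already enrolled continue on their regimen, and BID scans already done enter the by-cohort response summaries.

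A reader might also infer that a delayed BID patient gets a longer recorded PFS, because progression is found later. The document does not support that. As Step 4 shows, the written 53-day limits censor such patients at Day 1 or at the previous scan.

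**Conclusion.** The contradiction is real and stands in the current text. Once cumulative delay reaches about two weeks, the BID scan under footnote o falls largely outside the calendar window, and at three weeks wholly outside it. Scan timing then depends on toxicity, and SD can become PD in best response and disease control. That change is possible only for patients who progress in the gap; it is not a general shift.

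The effect on recorded PFS has no fixed direction: it is censoring under the limits as written, and later-dated events only if those limits were corrected.

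The size is small: at most 12 patients, in a descriptive analysis, with about one reclassified even if every one of them were delayed by three weeks. That figure rests on the exponential assumption and on assumed medians of 8 to 16 weeks. The day windows rest only on the protocol's own figures, with the first dose as day 0.

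**What to change.** 1. In Table 2 footnote o, replace the two cycle-based imaging sentences with the anchor that Table 3 footnote q already uses: every 8 weeks, plus or minus 1 week, counted from first dose. Add that dose delays do not move the scan.
2. Add BID to the calendar rule in Section 5.1.1, so that it agrees with the Table 2 header and Appendix E.
3. For BID scans already done on the cycle rule, list the actual scan week and report BID stable disease and disease control with that caveat.
4. Reconcile the 53- and 35-day limits in Section 8.4.6 with the 8- and 9-week scan intervals, since items 1 and 2 alone do not repair PFS.

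The cost is a few sentences of protocol text and one listing column. The scan interval stays at the nominal 8 weeks, and no dosing rule changes.

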4.1 Enrolment/screening period

Procedures will be performed according to the Study Plan described in [Table 2](#), [Table 3](#), and [Table 4](#). The screening period begins once the patient has signed the informed consent.

Consent may be taken prior to the 28-day window if required. The screening period will then start when the tumour sample is deemed acceptable by the central lab.

Subjects will be considered in screening/enrolment period until all screening assessments are completed and eligibility is confirmed.

